Postpregnancy Family Planning Choices in Public and Private Sectors in Kenya and Indonesia (PPFP Choices)

Study Protocol

Jhpiego

Unique Protocol ID: IRB00007462

October 5, 2017

Uploaded to Clinicaltrials.gov on November 2, 2017

JHSPH IRB Research Plan for New Data Collection

PI Name: [name]

Study Title: Postpregnancy Family Planning Choices in the Public and Private Sectors in Kenya and Indonesia

IRB No.: IRB00007462

PI Version No. / Date: Version 5/ October 2017

I. Aims of the Study: Describe the aims/objectives of the research and/or the project's research questions or hypotheses.

The primary goal of PPFP Choices is to generate actionable evidence that can be used to improve programmatic activities to address post-pregnancy family planning in the public and private-for-profit sectors, and the ultimate intent of this investment is to advance and scale up post-pregnancy FP. The primary research question is:

Research Question

What are the key determinants at service delivery, provider and client levels that influence the uptake of post-pregnancy family planning in the public and private health care sectors in Indonesia and Kenya?

Secondary study questions evaluate: the program's impact on postpregnancy family planning uptake; the feasibility and acceptability of introducing programmatic elements and new methods of postpregnancy family planning; and the potential for scaling up successful programmatic elements and interventions. A detailed list of secondary study questions can be found in [Appendix I](#).

II. Background and Rationale: Explain why this study is being done. Summarize briefly what is already known about the issue and reference previously published research, if relevant.

Family planning (FP) is important throughout an individual's and couple's reproductive life, and particularly during the time immediately following pregnancy. The provision of family planning following pregnancy is a life-saving intervention that not only prevents unintended pregnancies, but also improves postnatal outcomes for mothers and infants and perinatal outcomes in subsequent pregnancies [1][2]. The WHO recommends spacing pregnancies by 2 years or more following the delivery of a newborn, and at least six months following spontaneous or induced abortion [1][2]. However, these recommendations are not always followed.

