The population of women who will experience postabortion care was calculated differently. Since the current proportion of these women who take up an FP method after PAC has not been reliably determined in the two countries, we have assumed an estimate of 50% (assumption of 50% provides us a high sample size). After six months, we estimate that 40% of them will still be using the method, and thus we need a sample size of 243 women in the intervention group only, per country. This group will be recruited at baseline, and will include an adjustment of 20% to account for loss to follow-up. This sample size is adequate to detect a 10 percentage point change within a 95% two-sided confidence interval at 80% power. The research question for PAC clients is: what percentage of PAC clients who want to use a method of family planning are using a method six months after the premature end of pregnancy? With this question, we hypothesize that 80% who want a method will get a method.

Health Facility Assessments: Prior to implementation of the study, in order to reach adequate sample size, 18 facilities in Kenya (9 intervention and 9 control, which are each split into 5 public and 4 private-for-profit in each arm) and 8 facilities in Indonesia (4 intervention and 4 control, which are each split into 3 public and 1 private-for-profit in each arm) will be purposefully selected in collaboration with respective Ministries of Health.

IV. Participants:

Describe the study participants and the population from which they will be drawn. Specify the inclusion and exclusion criteria. If you plan to include children, note their ages and whether you will include children in foster care. Note if the participants are particularly vulnerable in terms of cognitive limitations, education, legal migration status, incarceration, poverty, or some combination of factors.

Participants will be selected based on their relationship to intervention and control facilities where the PPPF Choices project is being introduced.

Participants in this study fall into two distinct categories: 1) Key Informants, and 2) female clients who participate in Client Interviews, Focus Group Discussions, and In-Depth Interviews.

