Facility Audits: Data Analysis: Mapping of facilities will be visually analyzed to provide further understanding of structural issues that may influence perceptions and key behaviors. We will also utilize multi-level data analysis to explore the feasibility of IPPI using STATA. Select data from the client interviews will be combined with key facility level indicators for a multilevel analysis of the factors affecting intention to use and receipt of immediate post-pregnancy family planning methods.

[figure not shown]
Furthermore, triangulation across methods will help to ensure quality of study findings and offer opportunities for deeper insights into the study concepts [12]. Observations will also be collated with qualitative analysis results and used to strengthen themes identified through key informant data. In addition, a team approach to data analysis will be employed where different researchers provide feedback on emerging interpretations and analysis and check developing categories and concepts back against the original data. In this way, an “audit trail” will be used to help ensure trustworthiness of findings and gather input from multiple investigators [12].

5. Answer the following if they are relevant to your study design:

A. If the study has different arms, explain the process for assigning participants (intervention/control, case/control), including the sequence and timing of the assignment.

The study will employ a quasi-experimental mixed-method design; both quantitative and qualitative data will be collected at multiple time points. In coordination with the MOH, we will first identify an “intervention area” and a “control area” at County-level in Kenya and an “intervention area” and a “control area” at District-level in Indonesia. Within the “intervention areas,” we will identify intervention facility sites (six in Kenya and four in Indonesia) and match them with an equal number of control facility sites from the “control areas,” based on a list of predetermined criteria (e.g., service statistics and client demographics).

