All facilities in the “intervention area” will receive all facility level training and support interventions at the beginning of and throughout the study data collection period, while all facilities in the “control area” will be afforded the benefits of the interventions in a phased manner; in the last 6 months of the study timeline, after data collection activities are completed. This is demonstrated in the following graphic:

*Note: exact number of implementation sites TBD

- B. If human biospecimens (blood, urine, saliva, etc.) will be collected, provide details about who will collect the specimen, the volume (ml) and frequency of collection, how the specimen will be used, stored, identified, and disposed of when the study is over. If specimens will be collected for use in future research (beyond this study), complete the "Biospecimen Repository" section below.
N/A
- C. If genetic/genomic analyses are planned, address whether the data will be contributed to a GWAS or other large dataset. Address returning unanticipated incidental genetic findings to study participants.
N/A
- D. If clinical or laboratory work will be performed at JHU/JHH, provide the JH Biosafety Registration Number.
N/A
- E. If you will perform investigational or standard diagnostic laboratory tests using human samples or data, clarify whether the tests are validated and/or the lab is certified (for example is CLIA certified in the U.S.). Explain the failure rate and under what circumstances you will repeat a test. For all human testing (biomedical, psychological, educational, etc.), clarify your plans for reporting test results to participants and/or to their families or clinicians. Address returning unanticipated incidental findings to study participants.
N/A
- F. If your study involves medical, pharmaceutical or other therapeutic intervention, provide the following information:
 - a. Will the study staff be blind to participant intervention status?
N/A

- b. Will participants receive standard care or have current therapy stopped?
N/A
- c. Will you use a placebo or non-treatment group, and is that justifiable?
N/A
- d. Explain when you may remove a participant from the study.
N/A
- e. What happens to participants on study intervention when the study ends?
N/A
- f. Describe the process for referring participants to care outside the study, if needed.
N/A

VI. Data Security and Confidentiality Protections:

A. Personally Identifiable Information (PII):

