Supportive Supervision Records: The project will employ Jhpiego staff and a ministry of health representative or consultant to provide Supportive Supervision to intervention facility providers trained in implant service provision and counseling at project facilities. Supportive Supervision is a proven method for improving the quality of services offered by trained providers through guiding, helping, and encouraging staff to continue using the skills they learn through training. Regular Supportive Supervision visits will be conducted to each facility. During these visits, supervisors use a Supportive Supervision Checklist to monitor the quality of services provided. Quality will be measured against a set of performance standards developed at the national level with stakeholders from each country. The study team will use

Supportive Supervision Records to track whether or not services are improving at project facilities. Data will be linked to facilities to assess overall facility quality and help determine the impact of the intervention.

2. Provide an estimated sample size and an explanation for that number.

Family Planning Facility Registers: We estimate that roughly 15% of women who deliver at intervention facilities and 10% of women who deliver at control facilities will accept a method of postpartum family planning and that on average 30 women per month will deliver in each of the 62 project facilities over the course of the project. Therefore, we anticipate facilities will collect information about approximately 3,906 postpartum FP acceptor clients during the 30 months of the study. Furthermore, we estimate that approximately 50% of women receiving postabortion care at both intervention and control facilities will accept a method of postabortion family planning and that on average 12 women per month will receive PAC at the project facilities over the course of the project. Therefore, we anticipate facilities will collect information about approximately 4,680 postabortion FP acceptor clients during the 30 months of the study. Based on these estimates, we expect to collect de-identified service statistics for approximately **8,586 postpregnancy FP acceptor clients**.

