APPENDIX I. Secondary Study Questions

Study Theme	Question
Overarching Question	What are the key determinants at service delivery, provider and client levels that influence the uptake of post-pregnancy family planning in the public and private health care sectors in Indonesia and Kenya?
Programmatic Effort	
 • What programmatic inputs increase a woman's likelihood of accepting an FP method immediately postpartum or postabortion? • What are the costs associated with implementing such interventions? • What are the costs and programmatic efforts needed to scale up and sustain these interventions? • What are the barriers and facilitators for young women's accessing post-pregnancy FP services? • What are effective programmatic approaches to engaging the private sector to provide a full range of post-pregnancy family planning methods?
Feasibility	
 • What proportion of post-pregnancy women receive an FP method, according to standard, prior to discharge, among those who opted for an FP method, by age, type of client, timing and method? • To what extent was the health care system able to offer a full range of post-pregnancy FP methods within existing service delivery platforms? (Areas to be examined will include infection prevention, resources, practices, knowledge and skills, commodity supply chain management, labor and delivery staffing, workflow, etc.) • To what extent were the health care facilities offering appropriate and quality post-pregnancy FP counseling at all relevant time points (antenatal care, early labor, prior to discharge, follow-up visits)? • To what extent were providers able to provide, with technical quality, FP counseling and services within the immediate post-pregnancy period? • What are internal and external inputs that incentivize or disincentivize private sector facilities in the provision of post-pregnancy FP services?

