E. **Facility Audits Data Analysis:** Mapping of facilities will be visually analyzed to provide further understanding of structural issues that may influence perceptions and key behaviors. Aggregated country and district/county data from the baseline audits will be used to inform final program intervention design where possible. Additionally, select data from the client interviews will be combined with key facility level indicators for a **multilevel analysis** of the factors affecting intention to use and receipt of immediate post-pregnancy family planning methods, and to assess the overall success of the program.

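### With 8 Indonesian facilities and no small-sample method or cap on facility indicators in SAP A and E, default tests reject a null indicator about 12–20% of the time

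*SAP*

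**What the plan says.** The primary question (Protocol, section I) is "What are the key determinants at service delivery, provider and client levels that influence the uptake of post-pregnancy family planning". The quantitative link between facility characteristics and uptake is in SAP E: "select data from the client interviews will be combined with key facility level indicators for a" multilevel analysis of factors affecting intention to use and receipt of immediate methods. SAP A sends variables into a multilevel model for the same outcomes if their bivariate p-value is below 0.05. Neither section lists or limits the facility indicators, describes the random effects, or names a reference distribution for facility-level terms.

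On the number of facilities, Protocol III.B (Health Facility Assessments) gives "8 facilities in Indonesia (4 intervention and 4 control, which are each split into 3 public and 1 private-for-profit in each arm" and "18 facilities in Kenya (9 intervention and 9 control, which are each split into 5 public and 4 private-for-profit in each arm". Section V.C.5.A agrees for Indonesia but not for Kenya: "intervention facility sites (six in Kenya and four in Indonesia". The figure in XIII.A.2, "each of the 62 project facilities", belongs to the register review, not to the client-interview model.

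On delivery, V.C.5.A says of each intervention-area facility that it "will receive all facility level training and support interventions at the beginning of and throughout the study data collection period". Control facilities receive the package after data collection. Appendix I asks, as a secondary question, which programmatic inputs raise a woman's "likelihood of accepting an FP method immediately postpartum or postabortion".

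**The concern.** A facility indicator takes one value per facility at a given audit, so its coefficient is informed by the number of facilities and not by the number of women. Most multilevel logistic software refers such a coefficient to the normal distribution by default, which is a poor approximation with 8 facilities. An ordinary bivariate logistic screen is worse, because it treats each woman as independent evidence about a characteristic of her facility. The audits cover staffing, training and commodities (Protocol V.C.1), so there is no shortage of candidates.

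The second problem is bundling. If every intervention facility gets every facility-level input and no control facility gets any until data collection ends, a coefficient for having received one component is the same contrast as arm. At stake is whether chance findings are reported as service-delivery determinants in a study whose declared purpose is scale-up.

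**Working it through.** **Inputs.** From the documents: facilities 8 (Indonesia) and 18 or 12 (Kenya); two-sided 5%, 80% power, 10% v 15% and 6% v 10%, design effect 2.5, 30% attrition and 10% refusal (III.B); countries not compared (V.A), hence models by country. Assumed: ICC 0.0028 to 0.05; arm and sector both in the model; outcome rates of 10% and 6% borrowed from the sample-size section, since none is given for the SAP E outcomes.

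**1. The plan's own figures.** n = [1.96√(2p̄q̄) + 0.842√(p₁q₁ + p₂q₂)]² / (p₂ − p₁)² gives 685.6 → 686 for Indonesia and 720.9 → 721 for Kenya.
- Indonesia: 686 × 2.5 = 1715; 1715/0.8 = 2144.
- Kenya: 721 × 2.5 = 1803; 1803/0.8 = 2254.

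All match Table 4. They size the arm comparison; no figure is given for facility indicators.

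**2. Degrees of freedom.** df = facilities − facility-level parameters (intercept, arm, sector, one indicator = 4).

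| | df | critical t | P(\|t\|>1.96) |
|---|---|---|---|
| Indonesia, 8 | 4 | 2.78 | 12.2% |
| Kenya, 18 | 14 | 2.14 | 7.0% |
| Kenya, 12 | 8 | 2.31 | 8.6% |

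The last column is the size of a z test when between-facility variation dominates and its variance is estimated without bias. Maximum likelihood divides by 8 rather than 4, which inflates the Indonesian statistic by √2: P(|t₄| > 1.96/1.414) = 23.8%.

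**3. ICC implied by the plan.** 2144/4 = 536 women per facility; (2.5 − 1)/(536 − 1) = 0.0028. This is the low end of the range. At 536 women, ICC 0.01 would mean a design effect of 6.4, and 0.05 would mean 27.8.

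**4. Simulated size at nominal 5%.** Random-intercept logistic model with arm, sector and one null facility indicator; 0.7 × 0.9 = 63% of women retained; 500 runs for Indonesia and 200 for Kenya.

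| | ICC | Wald z | Same model, t on facility df | Bivariate logistic, no clustering |
|---|---|---|---|---|
| Indonesia, 8 | 0.0028 | 14.8% | 3.4% | 15.4% |
| | 0.01 | 18.0% | 9.4% | 33.2% |
| | 0.05 | 20.2% | 10.8% | 66.0% |
| Kenya, 18 | 0.006 | 9.0% | 6.0% | 16.5% |
| | 0.02 | 11.5% | 8.5% | 41.5% |

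Monte Carlo standard error is about 1 to 2 points.

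**5. Check on the unclustered screen.** Size = 2[1 − Φ(1.96/√DE)] with DE = 1 + (338 − 1) × ICC, where 338 = 536 × 0.63. ICC 0.0028: DE 1.94, 16%. ICC 0.01: DE 4.37, 35%. ICC 0.05: DE 17.85, 64%. These agree with the simulation. With all 536 women retained, the plan's design effect of 2.5 gives 21.5%.

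**6. Precision in Indonesia.** The variance of a facility log-odds is about ICC/(0.1 × 0.9) + 1/(338 × 0.1 × 0.9). At ICC 0.0028 this is 0.0311 + 0.0329 = 0.0640, so the standard error per SD of an indicator is √(0.0640/8) = 0.089. For 80% power on 4 df the true slope must be about 3.76 standard errors: an odds ratio of 1.40. The same steps give 1.66 at ICC 0.01, 1.96 at 0.02 and 2.77 at 0.05.

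**7. Bundling.** Under V.C.5.A, each indicator of receiving a package component is 1 in every intervention facility and 0 in every control facility during data collection. These columns are identical to each other and to arm, and arm is itself one area against one area in each country.

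**The case against.** The strongest reply is that SAP E leaves the model open. It does not say how many indicators enter, whether arm and sector are both included, or which reference distribution applies. SAP D allows provider performance to be folded into an overall facility-quality assessment, so a single composite is possible. This stands in part: sizes of 19% or 30%, which follow from 2 or 1 df, need three or four separate indicators that the SAP does not specify, and they are not relied on here. But 4 df is already the position with one indicator, and nothing in the SAP stops more from entering through the p<0.05 screen.

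Three audits are planned, and staffing or stock can change within a facility. That is true and helps estimation somewhat. However, the baseline audit falls in months 4–6, recruitment ends by month 24, and the year-three audit comes after Indonesian women's pre-discharge outcomes. The SAP does not say how audits are matched to women.

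A reader might infer that training indicators duplicate arm. For Indonesia the documents do not support this: sites with providers already trained in long-acting methods are a selection criterion in both arms (III.B), and Appendix II lists supportive supervision rather than training for method provision there. Only receipt of package components coincides with arm.

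Finally, the question also draws on registers, supervision records and qualitative work, triangulated under the SAP. That limits the weight any one coefficient carries, but it does not correct the coefficient's error rate.

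**Conclusion.** The point holds in a bounded form. In Indonesia, with one facility indicator beside arm and sector, a default Wald z test has a true size of about 12–20%, two to four times nominal. The maximum-likelihood limit of 23.8% shows that the upper end is not exaggerated. An unclustered bivariate screen runs at 15–66% over the assumed ICC range. In Kenya the Wald figure is about 9–12% with 18 facilities. Package components cannot be separated from each other or from arm by intervention status in either country.

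A reader might go further and infer that facility-level determinants cannot be estimated at all, or that no valid test exists. The documents do not support that. Four degrees of freedom remain, indicators such as staffing and commodities can vary within an arm, and a t reference brings the Indonesian size to about 3–11%. What is missing is a limit and a method. Nor do the documents say that the programmatic-inputs question rests on this model alone.

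The figures assume separate country models, the stated ICC range, and the borrowed outcome rates.

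**What to change.** In SAP A and E:

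- Do not apply the bivariate p<0.05 screen to facility-level indicators. Prespecify a short list, and say which audit each value comes from.
- Fit models by country, and test facility-level terms with a t reference on facility degrees of freedom or an equivalent small-sample correction. A t reference on a maximum-likelihood variance can still be liberal (up to about 11% here), so a method that also corrects the variance is preferable.
- In Indonesia, enter no more than one indicator at a time beside arm and sector, and report estimates with intervals as exploratory.
- In Kenya, keep the number of indicators small relative to the number of facilities, after reconciling 18 facilities (III.B) with six per arm (V.C.5.A).
- State that facility-level inputs delivered together cannot be separated.
- Client-reported receipt of components may be analysed as a supplementary association, using Interviews 0 and 1 in Kenya and Interview 1 with its supplements in Indonesia. Note confounding by prior interest in family planning and, in Indonesia, that antenatal care may have been at another facility.

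This needs no new data. The cost is SAP wording and a more modest claim about facility-level determinants.
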